2.0 TRIAL DESIGN

Phase II trial in which patients with metastatic solid tumors experiencing progression after first line standard chemotherapy or for which there is no standard chemotherapy, and for which pembrolizumab does not have an FDA or compendia listing approved indication, will receive pembrolizumab intravenously at a dose of 200 mg every 3 weeks.

The end points are the immune-related objective response rate (primary) and the 20-week immune-related progression-free survival rate (secondary). Availability of paraffin embedded tumor material and willingness to provide blood for plasma DNA mutational analysis will be required for enrollment, as well as standard acceptable organ function and no history of autoimmune disease or previous treatment with immune check-point inhibitors. CT assessment at baseline and after every 8 weeks will be obtained to measure immune-related objective response rates. Patients will continue treatment until tumor progression or intolerable toxicity.

Stratification based on FANCD2 foci formation in tumor material (see below) to evaluate potential differences in activity will be performed. Exploratory correlatives include evaluation of mutation load on tumor and cell free DNA analysis and of gut microbiome composition on fecal samples.

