6.0 METHODOLOGY

6.1 Entry Criteria

Diagnosis/Condition for Entry into the Trial

Patients with metastatic or recurrent solid malignancy who have progressed on first line standard of care treatment or for which defined standard of care does not exist. Patients for which pembrolizumab has an FDA approved indication and for whom pembrolizumab is covered by their insurance should receive standard commercial pembrolizumab and will not be eligible for this trial.

Subject Inclusion Criteria

In order to be eligible for participation in this trial, the subject must:

1. Be willing and able to provide written informed consent/assent for the trial.
2. Be \geq 18 years of age on day of signing informed consent.
3. Have measurable disease based on RECIST 1.1.
4. Be willing to provide consent for retrieval of archival tumor material tissue from a previously obtained core or excisional biopsy of a tumor lesion. Consent will also be given to obtain tumor material from any new biopsy or excision planned for standard of care during active participation in this trial or when documenting first tumor progression after pembrolizumab treatment.
5. Have a performance status of 0, 1 or 2 on the ECOG Performance Scale.
6. Have a tumor presentation at screening for which pembrolizumab does not have an FDA approved indication for commercial use (see Section 4.2). Those patients for which insurance is not available, or insurance denies pembrolizumab will be considered in a case by case basis.
7. Demonstrate adequate organ function as defined in Table 2, all screening labs should be performed within 15 days of treatment initiation.

Table 2. Adequate Organ Function Laboratory Values

System	Laboratory Value
Hematological	
Absolute neutrophil count (ANC)	$\geq 1,500 / \mu\text{L}$
Platelets	$\geq 100,000 / \mu\text{L}$
Hemoglobin	$\geq 9 \text{ g/dL}$ or $\geq 5.6 \text{ mmol/L}$ without transfusion or EPO dependency (within 7 days of assessment)
Renal	
Serum creatinine OR Measured or calculated ^a creatinine clearance (GFR can also be used in place of creatinine or CrCl)	$\leq 1.5 \times$ upper limit of normal (ULN) OR $\geq 60 \text{ mL/min}$ for subject with creatinine levels $> 1.5 \times$ institutional ULN
Hepatic	
Serum total bilirubin	$\leq 1.5 \times$ ULN OR Direct bilirubin \leq ULN for subjects with total bilirubin levels $> 1.5 \times$ ULN
AST (SGOT) and ALT (SGPT)	$\leq 2.5 \times$ ULN OR $\leq 5 \times$ ULN for subjects with liver metastases

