7.2 Subject Replacement Strategy

We anticipate enrollment of 39 patients for which tumor and toxicity assessments following pembrolizumab administration can be made. We will replace patients enrolled for which clinical trial discontinuation was performed prior to any administration of pembrolizumab or those for which pembrolizumab is discontinued due to acute hypersensitivity reactions during the first administration of pembrolizumab. An attempt will be made to assess tumor response in all enrolled patients as specified in the protocol. However, patients experiencing clinical deterioration after two doses of pembrolizumab, will be considered treatment failures and will count as tumor progression. These patients will not be replaced.

We are also expecting that 30% of the patients enrolled will be negative on the FATS1 assay, which will be conducted in batched analyses.

See section 6.1.1 and 12.0.1 for expansion cohort.

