12.0 SAMPLE CALCULATION AND STATISTICAL ANALYSIS PLAN

The primary endpoint is overall immune-related objective response rate. We expect that similar to mismatch repair deficient patients, the immune-related objective response will be at or above 40% in patients with functional FA deficiency (FATSI negative), and less than 10% in patients without either homologous recombination repair deficiency or mismatch repair deficiency. Patients with mismatch repair deficiency will be excluded from this trial. Based on our prior screening data, we anticipate that close to 30% of patients with solid tumors, depending on tumor type will be FA functionally deficient.

We will utilize a two-stage phase II trial design to detect an iORR of at least 20% in the whole population tested vs. the null hypothesis that the true iORR is at most 5%, representing a response by chance alone, or other infrequent unknown mechanism. Specifically, we will test the null hypothesis $H_0: \text{iORR} \leq 5\%$ vs. $H_1: \text{iORR} \geq 20\%$ with 90% power and a Type I error rate of 10%. The alternative hypothesis of 20% iORR represents a weighted average of the anticipated 40% response in FATSI-negative patients and 10% response in FATSI-positive, assuming a 3 to 7 ratio of these patient groups. Interim analysis requires that at least two of the first 20 evaluable patients enrolled have an objective response. If this occurs, we will accrue 19 additional patients for a total of 39. Overall rejection criterion of the null hypothesis is observing at least 4 responses.

The proposed two-stage design was chosen instead of the Simon Optimal or Minimax design because it has a larger first stage enrollment and thus a higher expected number of FATSI-negative patients in the interim analysis. Total enrollment of 39 patients is only slightly greater than that of the Simon designs but has the advantage of increasing the expected number of FATSI-negative patients. Additionally, the proposed design has a higher early stopping probability under the null hypothesis. The following table summarizes these operating characteristics.

Table 10:

Design	First stage enrollment	Expected		Total enrollment	Total expected FATSI-patients	Actual α	Power	Expected study size
		FATSI-patients, 1 st stage	PET					
Optimal	12	4	0.54	37	11	0.093	90.2%	23
Minimax	18	5	0.40	32	10	0.072	90.1%	26
Proposed	20	6	0.74	39	12	0.099	91.7%	25

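### Section 2.0 and Section 6.1 disagree on approved-indication patients, who count toward the 20 and 39 by default; separately, untested MMR-deficient tumors can enter although Section 12.0 says they are excluded

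*Combined protocol and SAP*

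**What the plan says.** **Approved indication.** Section 2.0 describes the population as tumors "for which pembrolizumab does not have an FDA or compendia listing approved indication", with no exception. The opening of Section 6.1 makes ineligible only "Patients for which pembrolizumab has an FDA approved indication and for whom pembrolizumab is covered by their insurance", so both conditions must hold. Inclusion criterion 6 starts with a plain requirement, "Have a tumor presentation at screening for which pembrolizumab does not have an FDA approved indication for commercial use", and then adds the exception: "Those patients for which insurance is not available, or insurance denies pembrolizumab will be considered in a case by case basis". It sets no criteria for that judgment and no cap. Section 6.1 does not mention compendia listings.

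**Who is counted.** Section 12.0 states: "Interim analysis requires that at least two of the first 20 evaluable patients enrolled have an objective response". It then goes to 39 patients and tests the response rate in everyone tested, against a null of at most 5% explained as "representing a response by chance alone, or other infrequent unknown mechanism". Section 7.2 reads: "We will replace patients enrolled for which clinical trial discontinuation was performed prior to any administration of pembrolizumab". The only other patients it replaces are those stopped for acute hypersensitivity at the first infusion. Neither section refers to indication status.

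**MMR deficiency.** Section 12.0 states: "Patients with mismatch repair deficiency will be excluded from this trial". Exclusion criterion 10 (Section 6.2) is narrower. It removes immunohistochemically proven cases, says the test is standard at the center for colorectal and endometrial cancer, and requires a documented negative result from outside referrals with those two cancers. Section 5.3.1 speaks only of leaving out MMR-deficient colorectal cancer. The endometrial expansion cohort (Section 6.1.1) requires a microsatellite result by immunohistochemistry or sequencing.

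**The concern.** The null rate is set for patients in whom a response would be chance or something rare and unexplained. A tumor for which the drug is already approved does not fit that description. Nor does an MMR-deficient tumor, for which Section 4.4 cites high response rates and which Section 5.3.1 sets apart because the trial is looking for another responsive subset.

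With a success threshold of four responses, one responder of either kind could decide the result. What is at stake is interpretation: whether a positive result describes the population in Sections 2.0 and 12.0. In addition, two screeners could each follow the protocol and decide differently about the same patient.

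**Working it through.** **1. Passages side by side.**

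| Patient | Section 2.0 or 12.0 | Section 6.1 or criterion 10 |
|---|---|---|
| FDA-approved indication, drug covered | Out (2.0) | Out |
| FDA-approved indication, uninsured or denied | Out (2.0) | Case by case |
| Compendia-listed indication only | Out (2.0) | Not barred |
| MMR-deficient, proven by immunohistochemistry | Out (12.0) | Out |
| MMR-deficient, untested, not colorectal or endometrial | Out (12.0) | Not caught |

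Rows 2, 3 and 5 conflict. Once treated, such patients meet no replacement rule in Section 7.2 (unless stopped for first-infusion hypersensitivity), so they count.

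**2. Reproduce the plan's figures.** Inputs from Section 12.0: continue if at least 2 of 20 respond; reject if at least 4 of 39 respond. With X1 ~ Bin(20, p) and X2 ~ Bin(19, p),

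P(positive) = P(X1=2)·P(X2≥2) + P(X1=3)·P(X2≥1) + P(X1≥4).

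At p = 0.05: 0.1887 × 0.2453 + 0.0596 × 0.6226 + 0.0159 = 0.0463 + 0.0371 + 0.0159 = 0.0993. At p = 0.20 the same formula gives 0.9165. Table 10 states 0.099 and 91.7%. Both agree.

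**3. One counted entrant, the other 38 at 5%.** If the entrant responds with probability r,

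P(positive) = r·A + (1 − r)·B,

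where A and B are the probabilities given that the entrant does or does not respond.

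- Entrant in stage 1: A = P(at least 1 of the other 19 in stage 1, and at least 3 of the other 38) = 0.27040. B = P(at least 2 of those 19, and at least 4 of the 38) = 0.09027.
- Entrant in stage 2: A = P(at least 2 of 20, and at least 3 of the other 38) = 0.18922. B = P(at least 2 of 20, and at least 4 of the 38) = 0.09455.

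| r | Source of r | Stage 2 entrant | Stage 1 entrant |
|---|---|---|---|
| 0.05 | null | 0.099 | 0.099 |
| 0.20 | assumed | 0.2×0.18922 + 0.8×0.09455 = 0.113 | 0.2×0.27040 + 0.8×0.09027 = 0.126 |
| 0.40 | assumed | 0.4×0.18922 + 0.6×0.09455 = 0.132 | 0.4×0.27040 + 0.6×0.09027 = 0.162 |
| 5/7 | Section 4.4, MMR-deficient non-colorectal | 0.7143×0.18922 + 0.2857×0.09455 = 0.162 | 0.7143×0.27040 + 0.2857×0.09027 = 0.219 |

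The 5/7 is itself imprecise: its exact 95% interval is 29–96%. The documents give no response rate for the approved-indication entrants this trial might admit, and no entry rate for either group.

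**4. What a sensitivity estimate would show.** Clopper-Pearson 90% limits are the 5% quantile of Beta(x, n−x+1) and the 95% quantile of Beta(x+1, n−x), not adjusted for the two stages. Suppose the trial just succeeds, 4/39 = 10.3% (3.6–22.0%), and one patient is dropped. If that patient responded, 3/38 = 7.9% (2.2–19.2%). If not, 4/38 = 10.5% (3.7–22.5%).

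**The case against.** Several points on the other side stand.

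- A reader might infer that nothing says whether case-by-case entrants count. Sections 12.0 and 7.2, read literally, count them. What is missing is an explicit statement and an analysis without them.
- Section 6.1 can be read as one rule with one insurance exception, so its internal tension is mild. The firm conflict is with Section 2.0. The FDA-approved pool is also narrow: Section 4.2 lists only melanoma, PD-L1-defined non-small cell lung cancer and head and neck cancer among solid tumors.
- A reader might infer that the type I error is inflated or Table 10 is wrong. Neither follows. The hypothesis concerns everyone enrolled, and at a true rate of 5% in that population the error is 9.9%. The wording about an infrequent mechanism can even be read as already covering a few such patients.
- Criterion 10 describes testing for two cancers but does not say that others go untested, and it could be meant as the working definition of Section 12.0's exclusion. The documents should say so if it is. Exclusion 14 and the withdrawal provision in Section 7.0 could remove a recognized case, but both are discretionary and neither detects an untested one.
- It is tempting to bar such entrants from the 20 and 39. That would depart from testing the whole population. It would also leave room for only one extra patient: 39 + 10 expansion patients = 49, against the upper figure of 50 in Section 1.0.

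None of this removes the conflicts between passages or the difficulty of reading a narrowly positive result.

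**Conclusion.** The concern holds as a conflict over eligibility with a consequence for interpretation; the sample-size calculation is not in error. One counted entrant, with all others at 5%, takes the probability of a positive result from 9.9% to 11.3–16.2% if that patient's response probability is 20–40% (assumed), or to 16.2–21.9% at 5/7. The low end is a stage 2 entrant and the high end a stage 1 entrant. With no entrant nothing changes, and zero is possible.

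A reader might rank one gap above the other. The documents give neither the number of case-by-case entrants nor the frequency of untested MMR deficiency, so no ranking is supported. Nor do they show which way such entrants would move the comparison by FATSI status, which Section 5.3.2 already calls exploratory.

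**What to change.** 1. Reconcile Section 2.0 with Section 6.1 and criterion 6, including compendia listings, and Section 12.0 with exclusion criterion 10.
2. Record indication status and any known MMR or microsatellite status at screening, before response is known.
3. Keep the primary test on the whole population with its stated cut-offs, and say explicitly that these entrants are counted.
4. Pre-specify a sensitivity response rate with exact 90% interval, overall and by FATSI status. It should drop all approved-indication entrants and all patients found MMR-deficient or microsatellite-high by available clinical testing or the planned sequencing, responders and non-responders alike. Report the number of unknown status.
5. Do not reuse the 2/20 and 4/39 cut-offs on the reduced set. With four patients dropped (two per stage) and the cut-offs unchanged, type I error would be 0.073 and power 0.875, so it would be a different test.

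The cost is wording, one screening field, one extra analysis, and a slightly wider interval at a comparable response rate. One limit remains: Section 3.4 plans to look at other repair mechanisms in blood and Section 5.3.2 plans tumor sequencing, but neither names an MMR or microsatellite call, so status may stay unknown for many tumors.

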Albumin	$\geq 2.5 \text{ mg/dL}$
Coagulation	
International Normalized Ratio (INR) or Prothrombin Time (PT)	$\leq 1.5 \times$ ULN unless subject is receiving anticoagulant therapy as long as PT or PTT is within therapeutic range of intended use of anticoagulants
Activated Partial Thromboplastin Time (aPTT)	$\leq 1.5 \times$ ULN unless subject is receiving anticoagulant therapy as long as PT or PTT is within therapeutic range of intended use of anticoagulants

^aCreatinine clearance should be calculated per institutional standard.

8. Female subject of childbearing potential should have a negative urine or serum pregnancy within 72 hours prior to receiving the first dose of study medication. If the urine test is positive or cannot be confirmed as negative, a serum pregnancy test will be required.
9. Female subjects of childbearing potential (Section 5.7.2) must be willing to use an adequate method of contraception as outlined in Section 5.7.2 – Contraception, for the course of the study through 120 days after the last dose of study medication.
10. Male subjects of childbearing potential (Section 5.7.1) must agree to use an adequate method of contraception as outlined in Section 5.7.1- Contraception, starting with the first dose of study therapy through 120 days after the last dose of study therapy.

Note: For 9 and 10, abstinence is acceptable if this is the usual lifestyle and preferred contraception for the subject.

6.1.1 Expansion Cohort.

Ten (10) additional subjects with the diagnosis of metastatic or recurrent endometrial carcinoma will be enrolled in the trial at the conclusion of regular enrollment with subject with the eligibility discussed in 6.1., and as per Sample size Calculation and Statistics Section (Section 12). The following will be necessary criteria for this expansion cohort.

1. Diagnosis of Endometrial Carcinoma or Sarcoma which is metastatic and has failed standard treatment or is recurrent, or for which standard chemotherapy is contraindicated or refused by patient.
2. Sufficient tissue is available for correlative studies as specified on Section 9.0.2.8.
3. MSI studies have been performed, either by immunohistochemistry or next generation sequencing and results show that patient is MS low or stable.
4. Patient meet all the inclusion criteria discussed above on 6.1 and none of the exclusion criteria discussed below on section 6.2.

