9. Has active autoimmune disease that has required systemic treatment in the past 2 years (i.e. with use of disease modifying agents, corticosteroids or immunosuppressive drugs). Replacement therapy (e.g., thyroxine, insulin, or physiologic corticosteroid replacement therapy for adrenal or pituitary insufficiency, etc.) is not considered a form of systemic treatment.
10. Has immunohistochemically proven mismatch repair deficient cancer (this test is standard in our center for colorectal and endometrial cancer patients, and documentation will be required to be negative to accept outside referrals with colorectal or endometrial cancer for this trial).
11. Has a history of (non-infectious) pneumonitis that required steroids or current pneumonitis
12. Evidence of interstitial lung disease.
13. Has an active infection requiring systemic therapy.
14. Has a history or current evidence of any condition, therapy, or laboratory abnormality that might confound the results of the trial, interfere with the subject's participation for the full duration of the trial, or is not in the best interest of the subject to participate, in the opinion of the treating investigator.
15. Has known psychiatric or substance abuse disorders that would interfere with cooperation with the requirements of the trial.
16. Is pregnant or breastfeeding, or expecting to conceive or father children within the projected duration of the trial, starting with the pre-screening or screening visit through 120 days after the last dose of trial treatment.
17. Has received prior therapy with an anti-PD-1, anti-PD-L1, or anti-PD-L2 agent.
18. Has a known history of Human Immunodeficiency Virus (HIV) (HIV 1/2 antibodies).
19. Has known active Hepatitis B (e.g., HBsAg reactive) or Hepatitis C (e.g., HCV RNA [qualitative] is detected).
20. Has received a live vaccine within 30 days of planned start of study therapy.

Note: Seasonal influenza vaccines for injection are generally inactivated flu vaccines and are allowed; however intranasal influenza vaccines (e.g., Flu-Mist®) are live attenuated vaccines, and are not allowed.

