9.0.2.9 Laboratory Procedures/Assessments

Laboratory tests for hematology, chemistry, urinalysis, and others are specified in Table 9.

Table 8. Laboratory Tests

Hematology	Chemistry	Urinalysis	Other
Hematocrit	Albumin	Blood	Serum β -human chorionic gonadotropin†
Hemoglobin	Alkaline phosphatase	Glucose	(β -hCG)†
Platelet count	Alanine aminotransferase (ALT)	Protein	PT (INR)
WBC (total and differential)	Aspartate aminotransferase (AST)	Specific gravity	aPTT
Red Blood Cell Count	Lactate dehydrogenase (LDH)	Microscopic exam (If abnormal results are noted)	Total triiodothyronine (T3)
Absolute Neutrophil Count	Carbon Dioxide		Free tyroxine (T4)
Absolute Lymphocyte Count	(CO_2 or bicarbonate)	Urine pregnancy test †	Thyroid stimulating hormone (TSH)
	Uric Acid		
	Calcium		
	Chloride		Blood and stools for correlative studies
	Glucose		
	Phosphorus		
	Potassium		
	Sodium		
	Magnesium		
	Total Bilirubin		
	Direct Bilirubin (If total bilirubin is elevated above the upper limit of normal)		
	Total protein		
	Blood Urea Nitrogen		

† Perform on women of childbearing potential only. If urine pregnancy results cannot be confirmed as negative, a serum pregnancy test will be required.

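### Table 2 prints the albumin eligibility limit in mg/dL, so the row as written excludes nobody; the value and unit need confirming and the cell correcting

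*Combined protocol and SAP*

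**What the plan says.** Section 6.1 lists what a subject must satisfy to enter. Inclusion criterion 7 reads "Demonstrate adequate organ function as defined in Table 2, all screening labs should be performed within 15 days of treatment initiation", so every row of Table 2 is an operative eligibility rule.

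The albumin row, which follows AST/ALT and precedes the coagulation rows, reads "Albumin $\geq 2.5 \text{ mg/dL". The hemoglobin row of the same table reads "\geq 9 \text{ g/dL}$ or $\geq 5.6 \text{ mmol/L}$ without transfusion or EPO dependency".

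Section 6.1.1 extends the rule to the 10 expansion patients with endometrial cancer: "Patient meet all the inclusion criteria discussed above on 6.1 and none of the exclusion criteria discussed below on section 6.2".

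Albumin appears once more, as a test name in the chemistry column of the laboratory list in Section 9.0.2.9, with no unit and no limit. No other section gives an albumin threshold.

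Section 6.2, exclusion 14, is the nearest related rule. It covers a subject who "Has a history or current evidence of any condition, therapy, or laboratory abnormality that might confound the results of the trial", and also conditions that would interfere with participation or make it contrary to the subject's interest, all in the treating investigator's opinion.

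**The concern.** A numeric eligibility limit is there to screen every patient in the same way. This one is in a unit so small that, read literally, it cannot screen anyone. The row looks like a safeguard but does no work as printed.

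What is at stake is agreement between the written criterion and what is done at screening. If staff apply the row as printed, the albumin screen is void. If they silently read a different unit, a patient turned away for low albumin did in fact meet the written criterion. Section 17.1, item f, asks for units always to be stated and conversions documented, so an unrecorded reinterpretation sits badly with the protocol's own data rules.

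**Working it through.** No sample size, power or error rate is involved. The check is a unit conversion and a comparison.

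**Inputs**
- Printed limit: 2.5 mg/dL (Section 6.1, Table 2).
- Conversion: 1 g = 1,000 mg.
- Range of adult serum albumin: not in the documents. Assumed to be about 1 g/dL (severe hypoalbuminemia) to 5 g/dL.

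**Step 1. Convert the printed limit.** 2.5 mg/dL ÷ 1,000 = 0.0025 g/dL. Since 1 L = 10 dL, this is 0.025 g/L.

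**Step 2. Put the assumed range in the printed unit.** 1 g/dL = 1,000 mg/dL; 5 g/dL = 5,000 mg/dL.

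**Step 3. Compare.**
- Lower end: 1,000 ÷ 2.5 = 400.
- Upper end: 5,000 ÷ 2.5 = 2,000.

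Every value in the assumed range clears the limit by a factor of 400 to 2,000.

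**Step 4. Stress the assumption.** Take an extreme 0.1 g/dL, one tenth of the assumed lower end. That is 100 mg/dL, and 100 ÷ 2.5 = 40, so the patient still passes by a factor of 40. The share excluded by the row is 0% across the assumed range and well below it.

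**Step 5. Look for a correct value elsewhere.** The laboratory list names the test only, the expansion cohort refers back to Section 6.1, and exclusion 14 gives no figure. Nothing in the documents overrides the printed cell.

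**Step 6. Misprint or extraction fault?** The text was read from PDF by a program, so the source page should be looked at. The hemoglobin row of the same table was read with g/dL, and a reading fault would have had to add a letter in this one cell. A misprint in the protocol is the likelier explanation, but the page itself must settle it.

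**The case against.** The strongest reply is that the misprint does little harm in practice, and much of that stands.

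- **Passing one row admits nobody.** A reader might infer that the protocol as written lets in patients with severe hypoalbuminemia. The documents do not support that as a consequence of this row alone. The bilirubin, AST/ALT, renal, hematological and coagulation limits and ECOG 0 to 2 still apply. Exclusion 14 removes a patient whose laboratory abnormality the investigator judges to matter. It does not repair the cell, however: it turns on individual opinion and states no albumin value.
- **Most screeners would probably read g/dL.** Anyone at or above 2.5 g/dL (2,500 mg/dL) is also above 2.5 mg/dL, so that reading could never enrol a patient who fails the printed rule. The only departure would be turning away someone literally eligible. The documents mainly describe one institution, so there is little evidence that sites would read the row differently.
- **Effect on the endpoints.** A reader might infer that frail patients would lower the immune-related response rate and raise early toxicity. Section 7.2 does count clinical deterioration after two doses as progression, without replacement, so some loss of response is conceivable. It would make rejection of the null harder, costing power rather than adding false positives. But the documents give no albumin distribution, no number affected and no link between albumin and either outcome, so this remains conjecture.

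None of this makes the printed row capable of excluding anyone.

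**Conclusion.** The point holds as a minor one. As printed, the albumin criterion is 0.0025 g/dL and excludes nobody, in the main trial and in the expansion cohort. This rests on one assumption from outside the documents, an adult range of about 1 to 5 g/dL, and it survives a tenfold reduction of the lower end.

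The factor of 1,000 is the ratio of mg to g. It should not be read as the distance from the limit to the lowest measurable albumin, for which the documents give no figure. Nor does it establish the intended limit: the hemoglobin unit makes a slip in the unit likely, but only the sponsor can confirm both value and unit.

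The two-stage design in Section 12.0 is unaffected. Its response thresholds (two responses in the first 20 evaluable patients, four in 39), error rate and power do not use this value.

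**What to change.** 1. Compare the Table 2 albumin cell with the source page of the protocol.
2. Have the sponsor confirm the intended value and unit. This review does not propose a limit.
3. Correct the cell so that the criterion binds. The expansion cohort needs no separate edit, because it refers back to Section 6.1.

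The cost is one table cell and a line in the amendment record. No design figure or analysis changes. The gain is a criterion that screens as intended and matches what is done at enrolment.
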